7.2.1.3 Visit 19 – Day 1 of the Open-Label Extension (Re-entry Subjects only)

This visit is only for those subjects who completed both Visits 16 and 17 during the Main Study.

- Review the inclusion and exclusion criteria.
- Reconfirm medical history, including past (prior to any narcolepsy treatment) and current symptoms of narcolepsy.
- Obtain weight in ordinary indoor clothes (without shoes).
- Obtain vital signs (systolic and diastolic blood pressure, heart rate and respiratory rate, and body temperature) in the seated position after the subject has been resting for at least 5 minutes
- Obtain a blood sample for electrolytes (Na, K, Ca, and Mg).
- Perform alcohol screen and urine drug screen.
- Obtain a urine pregnancy test for all females of childbearing potential (Section 6.10.1).
- Administer the:
 - C-SSRS Since Last Visit version.
 - PHQ-9.
- Record all AEs that occurred since the last visit on the AE eCRF.
- Record all concomitant medications that were taken since the last visit on the concomitant medications eCRF.
- Dispense study drug and provide instructions for dose administration.
- Schedule the next phone contact in 1 week.

Confidential Page 79 of 148

Clinical Trial Protocol: 15-006 Amendment 5

7.2.2 Open-Label Extension Period (Visits 20 to 32)

Subjects will include:

- Subjects who enter the Open-Label Extension directly from the Main Study (at Visit 16)
- Subjects who enter the Open-Label Extension after completion of the Main Study (at Visit 18) on Xyrem (alone or with an additional anticataplectic)
- Subjects who enter the Open-Label Extension after completion of the Main Study (at Visit 18) on non-Xyrem anticataplectic or not currently receiving treatment
- 7.2.2.1 Phone Contact –End of Week 1, 2, 3, 4, 5, 6, 7, 8, 9, and 10

Visits 20, 21, 22, 23, 24, 25, 26, 27, 28, and 29

- Assess tolerability, discuss dosing, and confirm compliance
- Record all AEs that occurred since the last visit or phone contact on the AE eCRF.
- Record all concomitant medications that were taken since the last visit or phone contact on the concomitant medications eCRF.
- Schedule the next phone contact or clinic visit.

7.2.2.2 Clinic Visit 30 – Week 12

- Obtain weight in ordinary indoor clothes (without shoes).
- Obtain vital signs (systolic and diastolic blood pressure, heart rate and respiratory rate, and body temperature), in the seated position after the subject has been resting for at least 5 minutes.
- Obtain a blood sample for electrolytes (Na, K, Ca, and Mg).
- Perform alcohol screen and urine drug screen.
- Collect any remaining study drug from prior visits and assess compliance.
- Assess tolerability, discuss dosing.
- Dispense study drug and provide instructions for dose administration.
- Obtain a urine pregnancy test for all females of childbearing potential (Section 6.10.1).
- Administer the:
 - C-SSRS Since Last Visit version.
 - PHQ-9
- Record all AEs that occurred since the last visit or phone contact on the AE eCRF.
- Record all concomitant medications that were taken since the last visit or phone contact on the concomitant medications eCRF.
- Schedule the Week 16 and 20 Phone Contacts (Visits 31 and 32).

Confidential Page 80 of 148

Jazz Pharmaceuticals

Clinical Trial Protocol: 15-006 Amendment 5

7.2.2.3 Phone Contact –End of Weeks 16 and 20

Visits 31 and 32

- Assess tolerability, discuss dosing, and confirm compliance
- Record all AEs that occurred since the last visit or phone contact on the AE eCRF.
- Record all concomitant medications that were taken since the last visit or phone contact on the concomitant medications eCRF.
- Schedule the next phone contact or clinic visit.

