5.6 Prior and Concomitant Therapy

5.6.1 Prohibited Concomitant Medications

In this study, the following medications are prohibited:

- a. Treatment with any central nervous system sedating agents including, but not limited to, benzodiazepines, non-benzodiazepine anxiolytics/hypnotics/sedatives, neuroleptics, opioids, barbiturates, phenytoin, and ethosuximide, or the MCT inhibitor valproate are prohibited during the study and must have been discontinued within 2 weeks prior to Day 1. (Discontinuation for the purpose of study enrollment is only permitted if considered safe by the Investigator and approved by the Medical Monitor.) If a subject undergoes short-term out-patient procedures during the study and requires opioids or benzodiazepine use, study drug may be held for one night while these drugs are given. If opioid or benzodiazepine use is required for multiple days, the subject should be discontinued from the study.
- b. Other anticataplectic therapies (e.g., SNRI, SSRI, TCA or atomoxetine) are prohibited during the Stable-Dose, Double-Blind, and Open-Label Extension Periods. For the Main Study, these therapies must have been tapered and discontinued during the cross titration in the Titration Period. (Discontinuation for the purpose of study enrollment is only permitted if considered safe by the Investigator and approved by the Medical Monitor.) For the Open-Label Extension, tapering and discontinuation must occur by Visit 30.
- c. Oral isotretinoin (Accutane) is prohibited during the study.
- d. Investigational drugs other than study drug are prohibited during the study.
- e. Stimulants or alerting agents are disallowed during the study for subjects who were not taking these medications at the start of the study.

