6.9 Patient Health Questionnaire-9 (PHQ-9)

The PHQ-9 is the nine item depression scale developed based on the nine diagnostic criteria for major depressive disorder in the DSM-IV (Diagnostic and Statistical Manual Fourth Edition). The instrument can be administered in person, by telephone, or can be self-administered and is used to facilitate diagnosis of major depression and assessment of symptom severity. It is validated and documented in a variety of populations and is available in a variety of languages (Appendix 6, Kroenke K et al. 2001). All subjects will be carefully monitored for emergent depression and suicidality. The subject will be evaluated and an assessment of risk will be made by a qualified mental health professional if major depression is suspected or active suicidal ideation is identified.

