6.13 Adverse Event Reporting

6.13.1 Adverse Events (AEs)

An AE is any untoward medical occurrence associated with the use of a drug in humans, whether or not considered related to study drug or procedure.

Adverse events include, but are not limited to: (1) a worsening or change in nature, severity, or frequency of conditions present at the start of the study (defined as Visit 1 and Visit 18 [Re-entry Subjects]); (2) subject deterioration due to primary illness; (3) intercurrent illness; (4) drug interaction; and/or (5) abnormal clinically significant laboratory values.

- Symptoms of the underlying medical condition narcolepsy are not considered as AEs unless there is an exacerbation of the subject's baseline symptoms at entry into the study. (Visit 1 and Visit 18 [subjects who re-enter the study for the Open-Label Extension]).
- Clinically significant adverse changes from baseline clinical status (Visit 1 and Visit 18 [subjects who re-enter the study for the Open-Label Extension]) in ECGs, routine laboratory tests, and physical examinations are considered AEs. Any subject complaint associated with such an abnormal finding will also be reported as an AE.

All AEs, whether observed by the Investigator, reported by the subject, determined from laboratory findings, or other means, will be documented.

For Re-entry Subjects (completed the Main Study), any new clinically significant condition not previously recorded as an AE during the Main Study and which occurred prior to obtaining informed consent for the Open-Label Extension, is considered medical history and should be documented as such (see Section 6.3).

Subjects should be questioned in a general way, without asking about the occurrence of any specific symptom. The Investigator should attempt to establish a diagnosis of the event based on signs, symptoms, and/or other clinical information. In such cases, the diagnosis, not the individual signs/symptoms, should be documented as the AE.

Following questioning and evaluation, all AEs, whether believed by the Investigator to be related or unrelated to the study drug or procedure, must be documented in the subject's medical records, in accordance with the Investigator's normal clinical practice. Each AE is to be evaluated for duration, severity (Section 6.13.2), seriousness (Section 6.13.3), and causal relationship to the study drug or procedure (see Section 6.13.4).

> Confidential Page 60 of 148

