Visits 4, 5, 7, 8, 9, and 11

- Record all AEs that occurred since the last visit or phone contact on the AE eCRF.
- Record all concomitant medications that were taken since the last visit or phone contact on the concomitant medications eCRF.
- Administer the PHQ-9 (Weeks 2, and 6 only).
- Discuss the frequency of cataplexy attacks with the subject and confirm that the Cataplexy Frequency Diary is being completed.
- Discuss dosing with the subject and confirm compliance; confirm that the Dosing Diary is being completed.
- Discuss tapering of anticataplectics with the subject (Groups 2 and 3 only).
- Assess control of cataplexy, EDS and tolerability to current dose.
 - All Pre-randomization Groups: If needed, continue titration of JZP-258 and provide instructions for dosing (titration up or down or staying on the current dose) until the next phone contact or clinic visit. JZP-258 dose adjustments are not allowed after Week 10.
 - Pre-randomization Groups 2 and 3: If further JZP-258 titration is not needed and the subject has remained on the same JZP-258 dose for the previous 2 weeks begin taper of the non-indicated anticataplectic.
 - Pre-randomization Groups 2 and 3: When taper of non-Xyrem anticataplectic is initiated, assess taper progress and advise subject on taper instructions, as appropriate.
 Anticataplectic taper must be completed by Week 10.
- Schedule the next phone contact or clinic visit.

CLINIC VISITS - END OF WEEK 4 AND 8 - VISITS 6 AND 10

- Obtain weight in ordinary indoor clothes (without shoes).
- Obtain vital signs (systolic and diastolic blood pressure, heart rate and respiratory rate, and body temperature), in the seated position after the subject has been resting for 5 minutes.
- Obtain a blood sample for electrolytes (Na, K, Ca, and Mg).
- Obtain a urine pregnancy test for all females of childbearing potential (Section 6.10.1).
- Perform alcohol screen and urine drug screen.
- Record all AEs that occurred since the last phone contact on the AE eCRF.
- Record all concomitant medications that were taken since the last phone contact on the concomitant medications eCRF.
- Administer:
 - C-SSRS Since Last Visit version.

Confidential Page 72 of 148

- PHO-9.
- Review Cataplexy Frequency Diary for completeness.
- Review the Dosing Diary for compliance with dosing.
- Assess control of cataplexy, EDS and tolerability to current dose.

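### No PHQ-9 or C-SSRS is scheduled between OLE Day 1 and Week 12, while re-entry subjects taper anticataplectics; the Main Study gives the PHQ-9 every two weeks during the same kind of taper.

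*Protocol*

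**What the plan says.** **Taper deadline.** Protocol 5.6.1(b) states: "For the Open-Label Extension, tapering and discontinuation must occur by Visit 30". Section 5.1.2.2 sets the same deadline. The drugs concerned are SNRIs, SSRIs, TCAs, atomoxetine and other anticataplectics, taken with or without Xyrem.

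**OLE assessments.** Section 7.2.1.3 (Visit 19, Day 1, re-entry subjects only) lists both the PHQ-9 and the C-SSRS. Section 7.2.2.1 then lists calls at the end of Weeks 1 to 10 ("Visits 20, 21, 22, 23, 24, 25, 26, 27, 28, and 29"). Their content is to "Assess tolerability, discuss dosing, and confirm compliance", to record adverse events and concomitant medications, and to schedule the next contact. Both scales return at "7.2.2.2 Clinic Visit 30 – Week 12". Appendix 1.2 marks neither scale at Visits 20 to 29. SAP 9.9.5.2 lists no PHQ-9 between OLE screening and OLE Week 12.

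**Main Study assessments.** At the calls in Section 7.1.2.3 the instruction is "Administer the PHQ-9 (Weeks 2, and 6 only"), with a further telephone PHQ-9 at Week 10 and clinic PHQ-9s at Weeks 4, 8 and 12.

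**Commitment.** Section 6.9 says "All subjects will be carefully monitored for emergent depression and suicidality" and allows the PHQ-9 to be given by telephone. The synopsis, under Safety Assessments, makes the same commitment for the duration of the study and names the PHQ-9 and the C-SSRS as the means.

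**The concern.** Depression and suicidality are risks that the protocol itself singles out. Both scales are safety endpoints (Section 9.9), suicide risk is a discontinuation criterion (6.14.1), and exclusion 18 concerns unsafe antidepressant withdrawal. The Main Study schedules a structured depression screen every two weeks while anticataplectics, most of them antidepressant classes, are withdrawn. The OLE asks some re-entry subjects to go through the same kind of withdrawal, but their first structured assessment after Day 1 falls at the taper deadline. No reason is given for the lighter schedule.

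Two things are at stake. A change in mood during the taper would have to be volunteered or noticed on a call, because no scheduled instrument would pick it up. And the OLE, added partly to assess longer-term safety (Section 3.1.3), would hold no PHQ-9 severity scores from the weeks in which these subjects stop their other medication.

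**Working it through.** The plan states no figure to reproduce. The check is a count of scheduled assessments, taken from Protocol 7.1.2 to 7.1.3 and 7.2.1 to 7.2.2 and compared with Appendices 1.1 and 1.2 and SAP 9.9.5.2.

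**Step 1. Assessment weeks, taking Day 1 as Week 0**

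- Main Study PHQ-9: 0, 2, 4, 6, 8, 10, 12 (Weeks 2, 6 and 10 by telephone).
- OLE PHQ-9, re-entry subjects: 0 (Visit 19), 12 (Visit 30).
- Main Study C-SSRS: 0, 4, 8, 12, plus Week 1 for subjects seen in clinic then (Groups 3 and 4 routinely; Groups 1 and 2 at the Investigator's choice).
- OLE C-SSRS, re-entry subjects: 0, 12.

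**Step 2. Number strictly between Day 1 and Week 12, and longest gap**

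| Scale | Main Study | OLE re-entry |
|---|---|---|
| PHQ-9, number between | 5 (Weeks 2, 4, 6, 8, 10) | 0 |
| PHQ-9, longest gap | 2 weeks | 12 − 0 = 12 weeks (84 days) |
| C-SSRS, number between | 2, or 3 with Week 1 | 0 |
| C-SSRS, longest gap | 4 weeks | 12 weeks |

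**Step 3. Where the taper falls.** In the Main Study the taper must be finished by Week 10, so five PHQ-9s (Weeks 2 to 10) fall within the period in which tapering can occur. In the OLE the deadline is Visit 30, which is also the next assessment. A taper that starts on or after Day 1 and meets the deadline therefore has no PHQ-9 while it is under way. The Main Study calls also carry an item to discuss tapering with Groups 2 and 3; the OLE calls carry none.

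**Step 4. Contacts already available.** There are 10 OLE calls in the window (Weeks 1 to 10). Placing the PHQ-9 on the calls at Weeks 2, 4, 6, 8 and 10 raises the number between from 0 to 5. The assessment weeks become 0, 2, 4, 6, 8, 10, 12, so the longest gap falls from 12 weeks to 2 (84 days to 14), with no added contact.

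**Step 5. SAP handling.** Table 2 maps unscheduled and early-termination OLE PHQ-9s after Day 1 and up to Day 127 to the Week 12 visit (scheduled Day 85). An unscheduled PHQ-9 during the taper would therefore be reported under Week 12, or displaced by the result closest to Day 85. The current windows have no place for results from the taper period.

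**The case against.** The strongest reply is that the OLE schedule agrees with itself and that other safeguards cover the interval. Much of this stands.

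- Section 7.2.2, Appendix 1.2 and SAP 9.9.5.2 agree on OLE PHQ-9 timing after Day 1. Section 6.8 requires the C-SSRS only at clinic visits, and the OLE complies. Section 6.9 sets no frequency. The tension is with the stated commitment and the Main Study standard, not between two schedules.
- Every weekly call records adverse events. Unscheduled visits are allowed at any time (Section 7.2), and Visits 23 and 27 may become clinic visits for supply reasons. A reader might infer that nothing scheduled could raise a suspicion of depression. That goes too far, because a volunteered complaint on a call could.
- A reader might also infer that the calls cannot screen for mood, because Section 6.13.1 says "Subjects should be questioned in a general way, without asking about the occurrence of any specific symptom". That sentence governs how adverse events are elicited. It does not bar a scheduled questionnaire, and Main Study calls under the same rule already carry the PHQ-9.
- Nor do the documents support saying that the suicide-risk discontinuation criterion cannot be met. Section 6.14.1 covers risk that is reported as well as risk assessed by the C-SSRS. The Visit 30 C-SSRS is the Since Last Visit version, so it asks about the interval, though only at the taper deadline.
- Main Study exclusions 1 to 19, including exclusion 18, are re-applied at Visits 18 and 19. Visit 18 also gives instructions for stopping excluded medications, so some withdrawal may begin before Day 1, between two PHQ-9s. These points reduce the risk but put no depression screen after Day 1.
- The taper argument does not reach rollover subjects, for whom other anticataplectics were already prohibited in the Stable-Dose and Double-Blind Periods. Nor does it reach the calls at Weeks 16 and 20, which come after the deadline.

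**Conclusion.** The concern holds for one group: re-entry subjects who begin the OLE on a non-Xyrem anticataplectic, alone or with Xyrem. For them, 0 PHQ-9 assessments are scheduled strictly between Day 1 and Week 12, against 5 in the Main Study, and the longest gap is 12 weeks against 2. What is missing is a structured depression screen during the taper, not all safety ascertainment.

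This rests on the taper taking place at least partly after Day 1, which the Visit 30 deadline allows, and on the scheduled calls not being converted to clinic visits. The number of subjects affected is not stated. They come from those who finished double-blind treatment before Amendment 4 was approved (Section 3.1.2.1) and then chose to re-enter, so the group may be small. The point is a low-cost improvement in safety measurement and does not touch the efficacy analysis.

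**What to change.** In Protocol 7.2.2.1 and Appendix 1.2, add the PHQ-9 by telephone to the existing calls at Visits 21, 23, 25, 27 and 29 (Weeks 2, 4, 6, 8 and 10) for re-entry subjects who are tapering an anticataplectic. Responses that raise a suspicion of depression or suicidality follow the evaluation pathway already in Section 6.9. Add these time points to SAP 9.9.5.2 and split the OLE PHQ-9 windows in SAP Table 2 so that taper-period scores are reported under their own visits. State in the protocol that the C-SSRS gap remains, because Section 6.8 ties that scale to clinic visits.

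In the same edit, reconcile Section 5.6.1(b), which prohibits other anticataplectics during the OLE and also allows their taper until Visit 30. No dose, taper rule, threshold or stopping rule is proposed here.

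Cost: a few minutes on each of five calls, a protocol amendment with ethics committee approval (Section 11.6), an eCRF change and the SAP edits. SAP 4.2 reports that full recruitment has been achieved, so the change helps only re-entry subjects who have not yet reached OLE Week 12; the documents do not say how many there are.

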7.2.3 End of Open-Label Extension or Early Termination

End of Week 24 – Visit 33 (or Early Termination)

- Perform a physical examination including a full examination of body systems (excluding a full genitourinary exam) and a brief neurological examination.
- Obtain weight in ordinary indoor clothes (without shoes).
- Obtain vital signs (systolic and diastolic blood pressure, heart rate and respiratory rate, and body temperature) after the subject has been resting for at least 5 minutes.
- Obtain fasting blood samples for serum chemistry (including Na, K, Ca, and Mg), hematology.
- Collect urine for urinalysis and perform urine drug screen.
- Perform alcohol screen.
- Provide for a light breakfast, if needed.
- Obtain a 12-lead ECG after the subject has been resting supine for at least 5 minutes.
- Obtain a urine pregnancy test for all females of childbearing potential (Section 6.10.1).
- Administer the:
 - C-SSRS Since Last Visit version.
 - PHQ-9
- Record all AEs that occurred since the last visit or phone contact on the AE eCRF.
- Record all concomitant medications that were taken since the last visit on the concomitant medications eCRF.
- Collect remaining study drug from Open-Label Extension and assess compliance.
- Instruct subject to follow-up with their healthcare provider regarding the resumption of any medications that were discontinued prior to study participation.
- Schedule the Safety Follow-up Visit in 2 weeks.

If a subject is withdrawn before completing the study, the reason for withdrawal will be entered on the appropriate eCRF. The specific reason for the withdrawal should be documented on the eCRF. For instance, rather than stating "withdrew informed consent", the specific reason for withdrawing the informed consent should be stated. Whenever possible and reasonable, the evaluations that were to be conducted during the final study visit should be performed at the time of premature discontinuation.

Confidential Page 81 of 148

It is vital to obtain follow up data on any subject who terminated because of an AE, abnormal laboratory test, or ECG finding. In any case, every effort must be made to ensure safety follow up procedures are completed.

7.2.4 Safety Follow-up Visit

End of Week 26 - Visit 34

- Obtain weight in ordinary indoor clothes (without shoes).
- Obtain vital signs (systolic and diastolic blood pressure, heart rate and respiratory rate, and body temperature) after the subject has been resting for at least 5 minutes.
- Obtain a urine pregnancy test for all females of childbearing potential (Section 6.10.1).
- Administer:
 - C-SSRS Since Last Visit version
 - PHQ-9.
- Record all AEs that occurred since the last visit on the AE eCRF.
- Record all concomitant medications that were taken since the last visit on the concomitant medications eCRF.

Unless any safety issues are identified that require follow-up, the study will be considered completed and the subject will be discharged from the study.

Confidential Page 82 of 148

Clinical Trial Protocol: 15-006 Amendment 5

8 QUALITY CONTROL AND ASSURANCE

The study will be conducted according to GCP guidelines and according to national law. Quality audits may be performed at the discretion of Jazz Pharmaceuticals.

Confidential Page 83 of 148

9 PLANNED STATISTICAL METHODS

9.1 General Considerations

Analyses may be provided either across the study or by study period (i.e., Optimized Treatment and Titration, Stable-Dose, Double-Blind Randomized-Withdrawal, and Open-Label Extension Periods) as appropriate to describe the efficacy and safety of JZP-258, and will be detailed in the statistical analysis plan (SAP). In general, for the Optimized Treatment and Titration, Stable-Dose, and Open-Label Extension Periods, results will be summarized by Pre-randomization Group and overall, and for the Double-Blind Randomized-Withdrawal Period results will be summarized by treatment group.

Categorical variables will be reported as frequency and percent. Continuous variables will be reported as number of subjects, mean, standard deviation (SD), or standard error (SE), median, minimum and maximum. All summaries, statistical analyses, and individual subject data listings described below will be completed using Version 9.3 or later of the SAS Statistical Analysis System (SAS Institute, Inc. Cary, NC).

